1.0 Background, Rationale and Context

In preparation for a full-scale randomized clinical trial (RCT) of an internet-delivered positive affect (PA) intervention for young adult cancer survivors, the EMPOWER study will collect pilot data on the feasibility and acceptability of a theoretically-driven, empirically-grounded, individual intervention to promote positive affect (PA).¹ An innovative, intervention for HIV patients (Lessons in Linking Affect and Coping: LILAC) will be adapted for use with young adult cancer survivors. This intervention teaches eight cognitive and behavioral skills to enhance PA, which may broaden and enhance an individual's resources for adapting to stressful events.² Feasibility and acceptability data will be collected with reports of daily positive and negative affect, general and domain-specific health-related quality of life, psychological well-being, and health behaviors. This will provide data to support further intervention studies, including an R01 proposal of a full-scale randomized clinical trial.

The number of people surviving cancer and even thriving with cancer grows annually. Historically, positive adjustment and growth in cancer has received little attention compared to impairment, disability and psychosocial morbidity. Today, this important area of research is demonstrating increased growth and interest^{3,4,5,6,7} with significant potential applications for cancer control and population sciences.⁸

A number of different psychosocial interventions have proven effective with cancer patients. The majority of these interventions are group-based and focus on alleviating the psychosocial burden of cancer by reducing or managing psychological distress.⁹⁻¹² Few interventions explicitly target PA. However, such interventions show promise for not only reducing the negative psychosocial impact of cancer and its treatment but for enhancing its positive psychosocial impact as well.¹³⁻¹⁶ A potential limiting factor of these PA interventions is that they are primarily group interventions targeted towards advanced cancer patients. Little is known about individualized PA interventions for cancer patients or survivors, but emerging and innovative research of a PA intervention for newly diagnosed HIV patients¹⁷⁻¹⁸ may have applications for cancer patients. Guided by Fredrickson's broaden-and-build theory of positive emotions²² and funded by the NIMH (R01MH084723), [name]'s RCT of a 5-session evidence-based intervention is designed to teach skills for increasing the frequency and intensity of daily PA and to examine the intervention's effects on subsequent psychological well-being, health behaviors, and physical health after diagnosis with HIV. Patients with HIV experience similar negative and positive psychosocial sequelae as patients with cancer.¹⁹⁻²² This manualized web-based and home-delivered intervention (LILAC) focused explicitly on increasing positive affect, and has shown good feasibility, acceptability, and preliminary efficacy in people coping with significant health-related stress^{23,24} including women with advanced breast cancer. Thus, [name]' empirically-based PA intervention research may have beneficial

ENHANCING MANAGEMENT OF PATIENT REPORTED OUTCOMES WITH EMOTION REGULATION (*EMPOWER*)

Comprehensive Cancer Center of Wake Forest University (CCCWFU)
CCCWFU 99516

parallels to inform this current project. In this application, we propose to build on this prior work to adapt the LILAC intervention to improve health-related quality of life (HRQOL) for young adult survivors of cancer.

2.0 Objectives

2.1 Primary Objectives

- 2.1.1 To adapt an individualized positive affect intervention that was developed for newly diagnosed HIV patients to use with young adult cancer survivors.
- 2.1.2 To pilot test the positive affect intervention with young adult cancer survivors to determine its feasibility and acceptability.

2.2 Secondary Objective

- 2.2.1 To describe health related quality of life, psychological well-being, and health behaviors in young adult cancer survivors

3.0 Study Population

60 young adult cancer survivors will be recruited through the Comprehensive Cancer Center of Wake Forest University (N=40) and the Robert H. Lurie Comprehensive Cancer Center of Northwestern University (N=20).

All patients will meet the following inclusion criteria:

- Able to read and understand English
- Past history of a cancer diagnosis (excluding basal cell skin carcinoma)
- 15 to 39 years of age at diagnosis of first cancer and currently between the ages of 18-39
- Within 0-5 years post-active treatment for initial diagnosis or recurrence
- Wireless internet connection or a home computer that is connected to the internet

Exclusion criteria:

- Currently receiving palliative or hospice care
- Significant psychiatric history

We anticipate a large percentage of our target sample to have active mywakehealth accounts, and we plan to use the secure MyChart portal to send study information to potentially eligible patients to gauge their interest in the study and communicate as necessary with consented participants.

ENHANCING MANAGEMENT OF PATIENT REPORTED OUTCOMES WITH
EMOTION REGULATION (*EMPOWER*)
Comprehensive Cancer Center of Wake Forest University (CCCWFU)
CCCWFU 99516

4.0 Methods

4.1 Registration Procedures

All patients entered on any CCCWFU trial, whether treatment, companion, or cancer control trial, **must** be registered with the CCCWFU Protocol Registrar or entered into ORIS Screening Log within 24 hours of Informed Consent. Patients **must** be registered prior to the initiation of treatment.

You must perform the following steps in order to ensure prompt registration of your patient:

1. Complete the Eligibility Checklist (Appendix B)
2. Complete the Protocol Registration Form (Appendix A)
3. Alert the Cancer Center registrar by phone, *and then* send the signed Informed Consent Form, Eligibility Checklist and Protocol Registration Form to the registrar, either by fax or e-mail.

*Protocol Registration is open from 8:30 AM - 4:00 PM, Monday-Friday.

4. Fax/e-mail ALL eligibility source documents with registration. Patients **will not** be registered without all required supporting documents.

Note: If labs were performed at an outside institution, provide a printout of the results. Ensure that the most recent lab values are sent.

To complete the registration process, the Registrar will:

- assign a patient study number
- register the patient on the study

4.2 Study Design

Patients will be recruited through RHLCCC and CCCWFU. Study staff will work with the Wake Forest Health Sciences Comprehensive Cancer Center's Cancer Informatics Group to identify potential CCCWFU patients from the electronic medical record and/or cancer registry. Potentially eligible patients will be recruited through a direct in-clinic approach as well as mailed letters followed by a phone call by a study team member. The recruitment call will be followed by an email

ENHANCING MANAGEMENT OF PATIENT REPORTED OUTCOMES WITH EMOTION REGULATION (*EMPOWER*)

Comprehensive Cancer Center of Wake Forest University (CCCWFU)
CCCWFU 99516

outlining the details discussed during the phone call and instructions on next steps and a link to the screening questionnaire (*Recruitment Email Script*). IRB-approved study flyers will be placed in the community at large, the Comprehensive Cancer Center at Wake Forest Baptist Medical Center and other strategic locations associated with Wake Forest Baptist Medical Center. IRB-approved study flyers may also be disseminated through email blasts or postings on websites of local cancer support agencies such as Cancer Services.

Patients will then be screened for eligibility using an online screening questionnaire on Qualtrics. Those that are ineligible will be displayed a message stating that he/she was ineligible. Patients who are eligible based will be navigated to the consent form and initial study questionnaire on Qualtrics, an online data collection tool that enables researchers to create study-specific websites for capturing patient data securely online. The instrument library includes self-report batteries or profiles from Patient-Reported Outcomes Measurement Information System (PROMIS) and the NIH Toolbox which include many of the measures that will be used in the study. At completion of the baseline questionnaire, all patients will be given access to the PA intervention.

The PA intervention is a 5 session online intervention that teaches 8 skills for increasing the frequency of positive emotions: 1) noting daily positive events²⁵⁻²⁸ 2) capitalizing on or savoring positive events;²⁹⁻³⁰ 3) gratitude;³¹⁻³³ 4) mindfulness;³⁴⁻³⁷ 5) positive reappraisal;³⁸⁻⁴⁵ 6) focusing on personal strengths;^{42-43,49-52} 7) setting and working toward attainable goals;^{53-54,55-58} and 8) small acts of kindness.⁵⁹⁻⁶³ The skills are presented over the course of 5 weeks. A week will consist of 1-2 days of didactic material and several days of brief, real-life skills practice and reporting, with each day's "home practice" taking approximately 20-30 minutes to complete. Patients cannot skip ahead, but they can return to old lessons or exercises if they choose. Most exercises are done in a "diary" format in which patients' past responses are displayed next to their new ones, so that every time the patient visits that exercise they see their growing list of past positive experiences. Patients will be permitted up to 8 weeks to complete this self-guided intervention to account for normal interruptions and unexpected delays in life.

Acceptability Interview. Research staff will conduct a 30-minute audio-recorded, post-intervention phone interview with all patients approximately one week after the intervention is complete to gather acceptability data. The semi-structured interview includes questions where participants rank the skill sessions in terms of favorite topics, the likelihood of referral to others (a friend or someone diagnosed with cancer) and the likelihood of practicing learned skills. There is also a section with open-ended questions, including questions about participant experiences with use of the website and home practice exercises

Patient Incentives. Each patient will be paid \$10 for each completed assessment for a maximum of \$30. Patients will be paid in full upon completion of the study via virtual gift card.

ENHANCING MANAGEMENT OF PATIENT REPORTED OUTCOMES WITH
EMOTION REGULATION (*EMPOWER*)
Comprehensive Cancer Center of Wake Forest University (CCCWFU)
CCCWFU 99516

Fidelity Monitoring. Whether patients understood and remember the intervention content will be assessed via multiple-choice "quiz" questions within each lesson. If patients are not able to answer a question, it will trigger a review of the relevant material (patients can also choose to review past material at any time). How frequently patients visit the website and how many times they complete the daily practice exercises for each skill will also be recorded. This information can be used in "dose-response" analyses to determine whether greater exposure to the exercises leads to stronger intervention effects. Patient progress will be monitored during the study and patients who appear to be having trouble or are disengaging from the intervention will be contacted. Our experience indicates that even very brief human contact can increase patients' commitment to the intervention. Patients will receive an email or phone call from a study staff member if they fail to visit the website more than 3 days in a week. Patients who cannot be reached or who do not resume visiting the website but also don't ask to leave the study will be re-contacted once per week for 3 weeks. After that they will be counted as non-completers, though we will still try to contact them to obtain post-intervention measures. Patients who do not reach the final lesson at the end of 8 weeks will also be considered non-completers and will be asked to take the post-intervention measures at that time.

5.0 Study Outcomes and Study Measures

Patients will complete self-report questionnaires at baseline (pre-test), approximately 8 weeks after baseline (post-test), then at 12 weeks (follow-up) for a total of 3 assessments, each lasting approximately 25-30 minutes. All measures will be completed from home via patients' personal computers. In addition to the measures listed below, key demographics will be assessed (race/ethnicity, education, household income, insurance status), cancer type, time since diagnosis, type of treatment, and time since treatment (See Appendix 3 for a complete list of measures).

5.1 Primary Outcomes

The primary outcomes for this study are measures of feasibility – accrual, refusal, retention, adherence and acceptability.

5.2 Secondary Outcomes

5.2.1 *Health-Related Quality of Life (HRQOL).* The PROMIS global health items will be used to assess overall HRQOL,⁶⁸ and the PROMIS-29⁶⁹⁻⁷⁰ to assess domain-specific aspects of HRQOL. The PROMIS Global scale consists of 10 items that assess general health, including overall physical and mental health. The PROMIS-29 consists of 29 items that assess physical functioning, anxiety, depression, fatigue, sleep disturbance, social

ENHANCING MANAGEMENT OF PATIENT REPORTED OUTCOMES WITH
EMOTION REGULATION (*EMPOWER*)
Comprehensive Cancer Center of Wake Forest University (CCCWFU)
CCCWFU 99516

functioning, pain interference, and pain intensity. These PROMIS measures will be supplemented with additional items from the PROMIS physical function short form⁷¹ and the PROMIS anger short form.⁷² The 4 PROMIS items for depression in this measure do not assess suicidality.

- 5.2.2 *Psychological well-being.*** Psychological well-being will be assessed with NIH Toolbox short forms for positive affect, life satisfaction, and meaning and purpose.⁷³ In addition, the NIH PROMIS General Self-Efficacy short form⁷⁴ will be administered as it is a closely related construct to psychological well-being and positively associated with better patient-reported outcomes.
- 5.2.3 *Health Behaviors.*** Healthy behaviors often associated with enhanced coping and better adjustment will be assessed.⁷⁵ Physical health behaviors will include: diet,⁷⁶ exercise,⁷⁷ alcohol consumption,⁷⁶ and cigarette smoking.⁷⁶

6.0 Statistical Considerations

Wake Forest School of Medicine will be the Coordinating Center for the study and will conduct all data analysis.

6.1 Analysis of Primary Objective

Accrual will be estimated as the number of patients accrued divided by the number of months of accrual. A 95% confidence interval for the monthly accrual rate will be calculated based on the Poisson distribution. The refusal rate will be estimated as the number of patients who refuse to participate divided by the number eligible. Retention will be primarily defined as the proportion of patients who provide 8 week and 12 week data. Patients who discontinue the intervention (refuse phone calls) but complete the outcome assessments will be counted in the numerator for calculating retention. Retention estimates will be calculated overall and by site. Adherence to the intervention will be calculated as the number of intervention sessions completed, the frequency of completing exercises, and number of website visits. We will calculate and report the mean adherence across all individuals as well as the proportion of patients who completed three or more sessions. Several measures will be used to quantify acceptability, including quantitative measures and interview. Means and the proportion responding affirmatively to the highest two responses for each question will be combined and exact 95% CIs will be calculated for these estimates. In addition, [name] and [name] will review open-ended (written) feedback and audio-recordings of phone interviews to identify meta-themes and determine saturation of concepts.⁷⁸

ENHANCING MANAGEMENT OF PATIENT REPORTED OUTCOMES WITH
EMOTION REGULATION (*EMPOWER*)
Comprehensive Cancer Center of Wake Forest University (CCCWFU)
CCCWFU 99516

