7.0 Data Management

The web intervention is delivered via a customized website built on Moodle, a courseware platform that is used by schools and universities worldwide. Moodle allows delivery of text or video instruction as well as interactive activities such as journals and adaptive quizzes. Moodle is recognized as secure and well-tested software, and HIPAA-compliant. All communications with the website will use industry-standard TLS/SSL encryption. Another layer of security will be provided by avoiding any use of personally identifiable information, medical information, or other sensitive information in the context of the intervention. Patients' Moodle accounts will not be linked to their real name or email address. The design of our intervention website has been refined through a number of iterations based on user testing and feedback from study patients (e.g., simplifying the interface,

ENHANCING MANAGEMENT OF PATIENT REPORTED OUTCOMES WITH
EMOTION REGULATION (*EMPOWER*)

Comprehensive Cancer Center of Wake Forest University (CCCWFU)
CCCWFU 99516

clearly labeling new material and exercises). We have also ensured that material is viewable on handheld, tablet, and laptop devices.

Informed consent document	ORIS
Protocol registration form	ORIS
Pre-, post- and follow-up test Questionnaires (Qualtrics)	Qualtrics
Intervention Sessions 1-5	Moodle
Phone Interview	Audio-recorded and stored among password protected study files

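### Does the refusal rate miss patients who decline before the online eligibility screener?

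*Combined protocol and SAP*

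**What the plan says.** Section 5.1 names five primary feasibility outcomes, of which refusal is one. Its full definition is in Section 6.1: "The refusal rate will be estimated as the number of patients who refuse to participate divided by the number eligible".

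Section 4.2 describes recruitment. Potential Wake Forest patients are first identified from medical records or the cancer registry. Then "Potentially eligible patients will be recruited through a direct in-clinic approach as well as mailed letters followed by a phone call" from a study team member. After the call comes an email "outlining the details discussed during the phone call and instructions on next steps and a link to the screening questionnaire". Next, "Patients will then be screened for eligibility using an online screening questionnaire on Qualtrics", and "Patients who are eligible based will be navigated to the consent form". Flyers, email and website postings (Section 4.2) and patient-portal messages (Section 3.0) are further routes, with no call described.

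Two procedures in Section 4.1 are tied to consent. Each enrolled patient must be registered or "entered into ORIS Screening Log within 24 hours of Informed Consent", and staff must "send the signed Informed Consent Form, Eligibility Checklist and Protocol Registration Form to the registrar". The table in Section 7.0 gives storage places for the consent form, registration form, three questionnaires, five intervention sessions and phone interview. It lists neither the screener nor a record of people approached.

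**The concern.** Suppose the number eligible means the number found eligible on the Qualtrics screener. A patient who says no in clinic or on the recruitment call never reaches the screener, and so enters neither the numerator nor the denominator. What is left is refusal at the consent page among people who had already agreed to be screened, and that group could be much more willing than those first approached.

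The Section 7.0 table adds to the worry. It points to a data source for accrual, retention, adherence and acceptability, but to none for refusal. The screening log and checklist in Section 4.1 are tied to consent, so they do not obviously cover decliners.

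The pilot exists to prepare a full-scale randomised trial (Section 1.0). A refusal rate that is too low would make that trial's recruitment look easier than it is.

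**Working it through.** **Inputs.** From the documents: 60 patients to be enrolled (Section 3.0), and precision for a proportion of ±12.7% at 60 patients and ±14.1% after 20% dropout (the Power and Sample Size section). No decliner counts are given, so the following are assumptions:

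- S: refusals after a patient is screened eligible
- C: declines in clinic or on the call, before the screener
- e: share of C who are in fact eligible

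**Step 1: the plan's own figures.** The worst-case 95% half-width is 1.96 × √(0.25/n). For n = 60 it is 12.65%; for n = 60 × 0.8 = 48 it is 14.14%. Both match the plan. Neither is a figure for refusal. At full accrual, any valid refusal denominator holds the 60 enrolled plus the refusers, so its half-width would be no wider than 12.65%. No stated number is wrong under either reading.

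**Step 2: three readings of the sentence.**

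- Screened patients only: S / (60 + S)
- All eligible patients, early decliners included: (S + eC) / (60 + S + eC)
- All decliners over screener-eligible patients: (S + C) / (60 + S)

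With S = 10:

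| C | Screened only | All eligible, e = 0.5 | e = 0.8 | e = 1 | All decliners over screened |
|---|---|---|---|---|---|
| 0 | 14.3% | 14.3% | 14.3% | 14.3% | 14.3% |
| 30 | 14.3% | 29.4% | 36.2% | 40.0% | 57.1% |
| 60 | 14.3% | 40.0% | 49.2% | 53.8% | 100% |
| 120 | 14.3% | 53.8% | 63.9% | 68.4% | 186% |

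For example, at C = 60 and e = 0.8, eC = 48 and the second reading gives 58/118 = 49.2%, against 10/70 = 14.3% for the first. The third gives 70/70 = 100%.

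The choice of reading can therefore matter a good deal, and its direction is not fixed. The first reading understates refusal among all eligible patients and the third overstates it. The third is also not a proportion, because its numerator is not contained in its denominator, so no competent analyst would use it.

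**Step 3: which reading the text supports.** Section 6.1 speaks of patients who refuse to participate and does not confine this to the consent page. The second reading fits those words without alteration. It needs a view on the eligibility of early decliners. At Wake Forest, Section 4.2 has potential patients identified beforehand from records, and several Section 3.0 criteria (cancer history, age at diagnosis, current age, time since treatment, palliative or hospice care) are of a kind a record can show. Where eligibility stays unknown, the e = 0.5 and e = 1 columns show how a report can bracket the answer.

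**Step 4: what the Section 7.0 table proves.** It is a short list of storage places and does not claim to be complete. It omits the screener, which Section 4.2 plainly describes, and the eligibility checklist, which Section 4.1 requires. Absence from the table does not show that a record will not be kept.

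**Step 5: an obvious rewording.** Decliners divided by decliners plus consenters would need no eligibility judgement. At S = 10 and C = 60 it gives 70/130 = 53.8%, the e = 1 value, whatever the true share eligible. It drops eligibility from the definition and so measures something other than what Section 6.1 sets out to measure.

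**The case for a change.** The best case for a change is about timing. Refusal is a primary outcome, recruitment has begun (18 patients in 6 months at Northwestern, Section 6.3, or 18/60 = 30% of the target), and a refusal not noted when it happens may be lost. Naming the step in Section 6.1 and adding a recruitment log to Section 7.0 would cost little. The record search in Section 4.2 is described for Wake Forest only, it finds potential rather than confirmed eligible patients, and nothing says that the list or the outcome of each approach is kept.

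Part of this stands. The plan does not name the step, no approach log is described, and at Northwestern the eligibility of early decliners may be unknown.

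The move from not described to not kept does not stand. The recruitment call is made by study staff, who learn of the refusal as it happens. Naming refusal as a primary outcome already commits the team to counting it, and Section 8.0 permits collection of what the outcomes need. The order of call then screener is explicit only for the letter-and-call route. In clinic it rests on one word of sequence, and flyer and portal recruits have no described call to refuse.

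**Conclusion.** The gap is real but is one of missing detail, and analysts can fill it within the existing words: count refusals from first approach, keep the numerator inside the denominator, say how eligibility was judged, and show the flow of patients. That is ordinary reporting for a pilot. The documents do not show that early decliners are left out or that their number cannot be recovered.

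The true size is unknown. Under the assumed counts above it runs from no difference (no early declines) to 14.3% against 49.2% (60 early declines, 80% eligible). Little in the plan depends on the result: the rate is descriptive, no progression rule uses it, and monthly accrual is calculated separately and is unaffected. The conclusion assumes that staff note refusals as they make contact, which the documents neither state nor contradict. No change to the plan is called for.

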6.2 Power and Sample Size

While this is a pilot study and we will not be testing the efficacy of the intervention, we do want to be able to estimate feasibility, acceptability, and changes in PA and PROMIS scores with a fair degree of precision. With a total of 60 patients we can estimate confidence intervals around means to within ± 0.25 SD, and proportions within $\pm 12.7\%$, with 95% confidence. Assuming that 20% of the patients may drop out, we could estimate confidence intervals for means within ± 0.28 SD and proportions within $\pm 14.1\%$ for measures evaluated at the end of the study. Furthermore, the sample size of $N=60$ should permit us to achieve data saturation, or the point at which successive information serves only to replicate previous content themes and no new information is obtained.⁷⁹ Past research reveals that saturation often occurs within the first 12 interviews.⁷⁸

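### Do refusal, retention and adherence need planned confidence intervals, given that N=60 is justified by interval width?

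*Combined protocol and SAP*

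**What the plan says.** Section 5.1 lists the primary outcomes as "accrual, refusal, retention, adherence and acceptability". Section 6.1 then takes them in turn:

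- **Accrual:** "A 95% confidence interval for the monthly accrual rate will be calculated based on the Poisson distribution".
- **Refusal:** "The refusal rate will be estimated as the number of patients who refuse to participate divided by the number eligible". No interval is mentioned.
- **Retention:** the proportion giving both 8-week and 12-week data. "Retention estimates will be calculated overall and by site". No interval is mentioned.
- **Adherence:** mean adherence is reported, "as well as the proportion of patients who completed three or more sessions". No interval is mentioned.
- **Acceptability:** means and top-two-response proportions, for which "exact 95% CIs will be calculated for these estimates".

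The Power and Sample Size section (the second of two sections numbered 6.2) says that efficacy will not be tested, but "we do want to be able to estimate feasibility, acceptability, and changes in PA and PROMIS scores with a fair degree of precision". For 60 patients it gives 95% margins of 0.25 SD for means and 12.7 points for proportions. After 20% dropout it gives 0.28 SD and 14.1 points. It also argues that 60 patients should be enough for qualitative saturation. Section 3.0 plans 40 patients at one site and 20 at the other.

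**The concern.** A pilot sized on interval width would be expected to report intervals for all its primary outcomes, and Section 6.1 provides for them in two of five. The reference to exact intervals closes a sentence about the acceptability questions and does not naturally reach back to retention or adherence. Accrual has its own interval sentence, so the authors specify intervals outcome by outcome, and their silence on the other three stands out.

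The whole-sample margins also do not transfer directly to two of these outcomes. Retention is broken down by site, where the denominators are 40 and 20. Refusal is divided by the number eligible, which is neither 60 nor 48.

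At stake is how the results are read. Section 1.0 says the data are to support a proposal for a full-scale trial, and retention feeds directly into enrolment planning. At 80% retention, 100 completers need 100/0.80 = 125 enrolled. Over the exact interval for 48/60 the number runs from 100/0.892, rounded up to 113, to 100/0.677, rounded up to 148. A bare percentage, especially one from 20 patients, would not convey that spread.

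**Working it through.** **Inputs.** N = 60, 20% dropout and 95% confidence (Power and Sample Size); site sizes 40 and 20 (Section 3.0). Retention of 80% is taken from the 20% dropout assumption. The documents give no refusal rate, so a range is assumed below.

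**1. The plan's own margins.** For a mean in SD units the half-width is 1.96/√n. For a proportion at the worst case p = 0.5 it is 1.96 × √(0.25/n).

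| n | Mean (SD) | Stated | Proportion (points) | Stated |
|---|---|---|---|---|
| 60 | 1.96/√60 = 0.253 | 0.25 | 0.98/√60 = 12.65 | 12.7 |
| 60 × 0.80 = 48 | 1.96/√48 = 0.283 | 0.28 | 0.98/√48 = 14.14 | 14.1 |

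All four agree to rounding.

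**2. Retention, exact (Clopper-Pearson) 95% intervals at 80%.**

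| Group | Count | Interval | Half-width (points) |
|---|---|---|---|
| Overall | 48/60 | 67.7% to 89.2% | 10.8 |
| Larger site | 32/40 | 64.4% to 90.9% | 13.3 |
| Smaller site | 16/20 | 56.3% to 94.3% | 19.0 |

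The overall figure lies inside the stated 12.7. The two site figures lie outside it, but the 12.7 is stated for a total of 60.

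**3. Adherence.** The denominator is all 60 patients, so the plan's figures apply as they stand: 0.25 SD for a mean, and at most 12.7 points for the proportion completing three or more sessions.

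**4. Refusal.** Assume that every eligible patient either enrols or refuses, and that 60 enrol. The number eligible is then 60/(1 − r).

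| Assumed r | Refused/eligible | Exact 95% interval | Half-width (points) |
|---|---|---|---|
| 30% | 26/86 | 20.8% to 41.1% | 10.1 |
| 50% | 60/120 | 40.7% to 59.3% | 9.3 |
| 70% | 140/200 | 63.1% to 76.3% | 6.6 |

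Every case is narrower than 12.7, so the larger denominator makes the stated margin cautious for refusal.

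**5. What writing in exact intervals would do.** Worst-case exact half-widths are 13.2 points at 30/60, 14.8 at 24/48, 16.2 at 20/40 and 22.8 at 10/20. The first two slightly exceed the stated 12.7 and 14.1, which are normal-approximation values. An instruction to use exact intervals would therefore set up a small mismatch with margins that are correct on their own basis.

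**The case for a change.** The strongest case for a change is that a sample-size statement is not an analysis instruction. It fixes neither the interval method nor what is reported by site. Three of five primary outcomes have no planned measure of uncertainty in a study whose stated aim is precise estimation, and one sentence would cure it without touching N or data collection. The smaller site's retention could vary by about 19 points either way at 80%, and up to 22.8 in the worst case, with no planned interval to show it.

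The omission stands, and so do these widths. The suggested consequence is weaker. The Power and Sample Size section already places feasibility among the things to be estimated with 95% intervals, so the intention is on record even though Section 6.1 does not repeat it for each outcome. Section 6.1 defines the numerator and denominator for refusal and retention, and nothing suggests that counts would be withheld. Given 16/20, any reader can recover 56.3% to 94.3%. The choice of method is also open to judgement: sessions completed is capped at five, and exercise and visit counts may be skewed, so a t interval is not an obvious default for mean adherence. That choice is reasonably left to the analyst.

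**Conclusion.** No change to the plan is needed. Section 6.1 leaves out intervals for refusal, retention and adherence, but this is missing detail and not an error. No stated number or rule is wrong: the four margins reproduce, they are claimed for the whole sample only, and interval width is accompanied by a qualitative saturation argument for N. Following the plan as written gives sound point estimates, with no bias, no lost data and no test or decision rule affected.

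The stated margins hold for overall retention at 80% (10.8 points against 12.7) and for refusal across the assumed 30% to 70% (10.1 to 6.6 points). Only by-site retention is wider, at 13.3 and 19.0 points, and the plan makes no precision claim there.

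The conclusion assumes that counts are reported with the percentages and that the analysts add these standard intervals at reporting, which is likely for a team that justified its sample size by interval width. The retention figures rest on the plan's 20% dropout. The refusal figures rest on assumed rates and on every eligible patient either enrolling or refusing.
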